5.4 Scientific Rationale for Study Design

5.4.1 Rationale for One Year Duration of Treatment

There is no consensus about the optimal treatment duration for patients in the adjuvant setting. For trials of interferon, various treatment frequencies and durations have been investigated (ranging between 6 months and 5 years).^{18,19} There is a significant geographic variability in the duration of interferon therapy, usually ranging between 1 and 1.5 years throughout the world. In order to minimize toxicity leading to discontinuation of study drug while maintaining expected efficacy of the study drug, the decision was reached to limit the duration of study therapy of nivolumab on CA2096GE to 1-year maximum duration. This is supported by data from CA209238, which was approved for nivolumab as adjuvant treatment of melanoma.

[figure not shown]
5.4.2 Rationale for Part 1 Endpoints and Non-Inferiority Margin

Not applicable per Protocol Amendment 01. The following information refers to the original study design.

PK co-primary endpoints for Part 1 of this study are Cavgd28 and Cminss. The co-primary endpoints would help to establish PK non-inferiority between the 2 different routes of administration (SC [REDACTED] and IV). The use of co-primary PK endpoints will provide data on exposure to nivolumab at different time points during treatment. Cavgd28 is the time-averaged concentration over the first 28 days of dosing and represents an early measure of exposure. The Cminss endpoint is a steady-state measure of exposure that can be used to assess accumulation with repeat dosing and as surrogate for long-term administration with [REDACTED]. Blood sampling time points have been selected to adequately characterize the co-primary PK endpoints (Cavgd28 and Cminss) while minimizing the burden to patients and HCPs.

Non-inferiority of [REDACTED] to Nivo IV will be concluded if the lower limit of the 2-sided 90% CIs for the ratio of geometric means for nivolumab (SC vs IV) Cavgd28 and Cminss is not lower than 0.8; as this criterion is consistent with regulatory advice.

Non-inferior PK exposures at early and late time points, particularly when the dose administration is given by the participant (instead of HCP), ensure effective drug levels are maintained over time and provide pharmacologic surrogate of disease control similar to approved Nivo IV.

5.4.6 *Rationale for Inclusion of Clinical Outcome Assessments/PROs (Part 1)*

Not applicable per Protocol Amendment 01. The following information refers to the original study design.

[figure not shown]
The evaluation of clinical outcomes assessments (COAs) such as patient-reported outcomes (PROs) is an increasingly important aspect of clinical efficacy and safety in oncology trials. Such data provide an understanding of the impact of treatment from the participant's perspective and offer insights into patient experience that may not be captured through physician reporting. Additionally, generic health-related quality of life (HRQoL) measures provide data needed for calculating utility values to inform health economic models.

To explore overall participant self-confidence with SC injection the Self-Confidence domain of the Self-Injection Assessment Questionnaire (SIAQ) will be used in the Part 1 Arm A (SC arm) only. Participant satisfaction with route of administration (IV versus SC) will be assessed using a modified version of the Cancer Treatment Satisfaction Questionnaire (CTSQ), namely the Satisfaction with Cancer Therapy domain. The Functional Assessment of Cancer Therapy - General 7 item version (FACT-G7) will be used to evaluate HRQoL. The FACT-G7 has been shown to be a valid, reliable, and rapid measure for monitoring symptoms and concerns in oncology practice and research. A modified version of the Treatment Administration Satisfaction Questionnaire (TASQ) will be used to assess Satisfaction, Physical Impact, Psychological Impact, Impact on Activities of Daily Living, and Convenience between IV and SC Routes of Administration. The EuroQol-5 Dimension-5 Level (EQ-5D-5L) will be used for economic evaluations and overall health status.

5.4.7 *Rationale for Open Label*

The expected incidence of AEs with nivolumab have been extensively studied and defined in prior clinical trials and are not expected to differ based on route of administration or delivery systems, (when not considering injection site reactions or procedure related AEs) as further demonstrated by the preliminary safety data from the nivolumab SC injection study, CA2098KX; therefore, an open-label approach is justified. In addition, the technical challenges associated with blinding favor the open-label design. The BMS study team will not conduct aggregate analyses by treatment group prior to pre-specified database locks (Sponsor blind approach).

5.5 *Justification for Dose*

[figure not shown]

[figure not shown]
Protocol Amendment No.: 01

[figure not shown]
Date: 25-May-2023

[figure not shown]
65

[figure not shown]
Approved v2.0 930174717 2.0

[figure not shown]
5.5.2 *Rationale for Dosing Regimen - Intravenous (Arm B)*

[figure not shown]
Nivolumab monotherapy was originally approved as a body weight-based dose of 3 mg/kg IV Q2W and was recently updated to flat-dosing regimens of 240 mg Q2W or 480 mg Q4W in multiple indications. For this study, the selected dose of 240 mg via IV Q2W is per dose/schedule approved for this patient population. In addition, there is extensive PK, safety, and efficacy data available at this dose across multiple tumors and dosing regimens. Global development with flat doses of nivolumab are ongoing in a broad range of clinical trials in a variety of additional tumor types. Based on the aforementioned nivolumab 240 mg IV Q2W is considered an appropriate and globally accepted comparator to [REDACTED]

In relation to transition to 480 mg IV Q4W, most recently, data from the comparator arm in study CA209915 support that the activity of flat dose (480 mg IV Q4W) nivolumab performs similarly to the originally assessed 3 mg/kg IV Q2W dosing schedule in study CA209238.

Additional details on nivolumab posologies and risk-benefit can be found in the BMS-936558 investigator brochure.

[REDACTED]

5.5.4 *Rationale for Switch from Q2W to Q4W (Arm B [IV])*

In order to mitigate participant burden, a switch from Q2W to Q4W will occur after Cycle 5 for participants in Arm B receiving IV nivolumab. Cycle 5 has been selected as the time for the switch as it was the time at which the primary endpoints in the original study design were being collected.

5.5.5 *Rationale for Continued Adjuvant Therapy for Participants Who Are Diagnosed with Melanoma in Situ During Study Treatment*

Malignant melanoma in situ (MMIS) Stage 0 includes Tis, N0, M0, demonstrates a radial growth phase in which the proliferation of malignant melanocytes is confined to the epidermis. Patients with a new Stage 0 melanoma are at minimal risk from that new tumor. The risk of death develops from advanced Stage IIIB/C/D or Stage IV melanoma for which they are receiving treatment during the clinical trial. Opdivo (nivolumab) is approved for the adjuvant treatment of adult patients with melanoma with involvement of lymph nodes or metastatic disease who have undergone complete resection. Consequently, in the absence of intolerable toxicity, patients with diagnosed MMIS should continue adjuvant therapy using the same dose and schedule for their original melanoma for a maximum of 1-year total duration starting from first dose (maximum of 13 doses). Melanoma in situ will not be considered a new primary malignancy.

5.5.6 *Safety/IMG with SC Nivolumab + rHuPH20*

In the Phase 1/2 CA2098KX study, the safety profile of Q2W and Q4W nivolumab SC monotherapy in participants with advanced/metastatic cancer was evaluated. The preliminary review of the study safety data showed that nivolumab SC vial and syringe across all studied doses was safe, tolerable, and manageable with an AE profile consistent with nivolumab when administered via IV.

- Sixty-seven participants in Part A (Group 1) and Part B (Group 2, 3, 4) received 1 SC nivolumab dose (720 mg or 960 mg) with or without rHuPH20 followed by IV nivolumab. Upon selection of the dose, 28 of these participants who were still on study at the time of the amendment, transitioned to SC nivolumab 1,200 mg + rHuPH20 Q4W (Part C)
- Thirty-six participants in Part D received SC nivolumab dose of 1,200 mg + rHuPH20 Q4W from the beginning of therapy
- Thirty-six participants in Part E received SC nivolumab dose of 600 mg + rHuPH20 Q2W from the beginning of therapy

Part A/B: Participants received single-dose SC nivolumab, either 720 mg (with or without rHuPH20) or 960 mg (with or without rHuPH20): The safety data from single-dose SC nivolumab followed by IV (Cycle 2+) included treatment-related AEs and SAEs previously reported within the Nivo IV IB with the exception of SC local reactions.³⁴ With respect to local AEs reported with SC injection, the local site reactions were low incidence, of low grade, and manageable.

Part C (transitioning to 1,200 mg + rHuPH20 from prior single-dose SC and IV): Interpretation of treatment-related AEs in Part C was difficult and clear attribution of systemic treatment-related AEs to SC nivolumab (vs IV) was not possible given switching between formulations and the long half-life of nivolumab.

Of the 28 participants that transitioned from Part A/B to Part C, any Grade AEs after transitioning to SC nivolumab were reported in 26 (93%) participants. Treatment-related AEs were reported in 16 (57%) participants after transitioning to Part C, all of which were Grade 1 to 2. In the majority of participants, low-grade treatment-related AEs were reported in the general disorders and

administration site conditions and skin and subcutaneous disorders SOCs. Within the general disorders and administration site conditions SOC, there were 3 (33.3%), 2 (33.3%), 3 (60.0%), and 1 (12.5%) participants that were reported with low-grade treatment-related AEs in Groups 1, 2, 3, and 4, respectively. Within the skin and subcutaneous disorders SOC, there were 2 (22.2%), 1 (16.7%), 0 (0.0%), and 1 (12.5%) participants that were reported with low-grade treatment-related AEs in Groups 1, 2, 3, and 4, respectively. No participants were reported to develop new or worsening Grade 3 or higher treatment-related AEs, and there were no reported treatment-related AEs leading to discontinuation or death.

Part D (1,200 mg + rHuPH20): Any grade AEs were reported in all 36 participants, of these there were 17 (47.2%) reports of Grade 3 to 4 AEs and 4 (11.1%) reports of Grade 5 AEs. Any grade treatment-related AEs were reported in 28 (77.8%) participants; of these there were 6 (16.7%) reports of Grade 3 to 4 treatment-related AEs. Treatment-related SAEs were reported in 3 (8.3%) participants, all were Grade 3 to 4. In the majority of participants, treatment-related AEs were reported in the general disorders and administration site conditions, skin and subcutaneous disorders, and endocrine disorders SOCs. Within the general disorders and administration site conditions SOC, there were 16 (44.4%) participants that were reported with low-grade treatment-related AEs. Within the skin and subcutaneous disorders SOC, there were 12 (33.3%) participants that were reported with low-grade treatment-related AEs, of these there were 3 (8.3%) reports of Grade 3 to 4 treatment-related AEs. Within the endocrine disorders SOC, there were 10 (27.8%) participants that were reported with low-grade treatment-related AEs. Of the reported treatment-related AEs, 4 participants (11.1%) were reported with AEs leading to treatment discontinuation. There was no reported treatment-related AE leading to death. No dose-related safety concerns were noted. Results to date suggest that SC nivolumab with rHuPH20 is safe and well-tolerated, which supports further clinical investigation.

Part E (600 mg + rHuPH20): In 36 participants, any grade AEs were reported in 27 (75.0%) participants; of these there were 10 (27.8%) reports of Grade 3 to 4 AEs, and 1 (2.8%) report of a Grade 5 AE. Any grade treatment-related AEs were reported in 20 (55.6%) participants; of these there were 3 (8.3%) reports of Grade 3 to 4 treatment-related AEs. There was 1 (2.8%) report of a treatment-related SAE of Grade 3 to 4. In the majority of participants, treatment-related AEs were reported in the skin and subcutaneous disorders and general disorders and administration site conditions SOCs. Within the skin and subcutaneous disorders SOC, there were 10 (27.8%) participants that were reported with low-grade treatment-related AEs. Within the general disorders and administration site conditions SOC, there were 9 (25.0%) participants that were reported with low-grade treatment-related AEs. There were no reported treatment-related AEs leading to discontinuation or death.

Across treatment groups, ADAs were reported with nivolumab (BMS-986298) with and without rHuPH20 similar to what has been reported with the IV formulation. In Part C, 15 out of 67 participants had positive treatment-emergent ADA for nivolumab (7 out of 22 [31.8%]) participants in the nivolumab 720 mg with rHuPH20 group, 5 out of 18 (27.8%) participants in the nivolumab 720 mg without rHuPH20 group, and 3 out of 10 (30%) participants in the nivolumab 960 mg with rHuPH20 group; there was no treatment-emergent ADAs in the 17 participants who

received nivolumab 960 mg without rHuPH20 group. One out of 22 (4.5%) participants in the nivolumab 720 mg with rHuPH20 group was classified as persistent positive ADA. In Part D, 1 out of 26 (3.8%) participants developed treatment-emergent ADA; however, none were persistent positive. No neutralizing ADAs were detected in any part of the study and no association of anti-nivolumab antibody development with select AEs (ie, bronchospasm, hypersensitivity, infusion-related reactions) was reported. Data do not suggest that the presence of ADAs with SC nivolumab impacts clinical safety (eg, injection site or hypersensitivity reactions). Overall, the PK, safety, and immunogenicity data further support clinical development of additional dosing schedules [REDACTED] and 600 mg Q2W) of SC [REDACTED] nivolumab.

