3.3.3 Nivolumab Overall Benefit/Risk Conclusion

The Sponsor will evaluate the benefit/risk profile of the study on an ongoing basis. This evaluation will be based on all available data with particular attention to [REDACTED]

[REDACTED] safety trends in this or any other clinical study of BMS-986298 or BMS-936558 whose severity and/or frequency suggest that participants would be exposed to an unreasonable and significant risk of illness or injury.

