5 STUDY DESIGN

5.1 Overall Design

Study CA2096GE is a multicenter, open-label, Phase 3 study. **Per Protocol Amendment 01, PK co-primary endpoints, secondary endpoints, [REDACTED] of the study have been removed. Efficacy, PROs, and biomarker analyses will not be completed. Samples already collected for PK and immunogenicity assessments will be analyzed bioanalytically for nivolumab concentrations and ADAs and reported as listings. Further collections for PK, ADAs, biomarkers, and PROs will be discontinued. Only safety assessments will be conducted.** Therefore, the study design has been adapted to reflect the Protocol Amendment 01 changes, [REDACTED]. Part 1 is no longer hypothesis-driven, but rather descriptive in nature (Arm A and Arm B), with the primary objective being safety and tolerability and exploratory objective as described in [Table 4-1](#).

- Arm A (n = 6):

- [REDACTED]

[figure not shown]
- Arm B (n = 8):

- Nivo IV (BMS-936558) 240 mg Q2W for Cycles 1 through 4.
 - Nivo IV 480 mg Q4W Cycle 5 onwards for up to total of 52 weeks.
 - All dosing will be performed in-clinic.

Participants will be stratified by stage (Stage IIIA/B vs Stage IIIC/D/IV) per AJCC 8th edition [REDACTED]

All participants will be treated until recurrence of disease, unacceptable toxicity, participant withdrawal of consent, death, or a maximum of 52 weeks of treatment from first dose, whichever occurs first.

The study design schema is presented in [Figure 5.1-1](#).

Figure 5.1-1: Study Design Schema

Abbreviations: AJCC, American Joint Committee on Cancer; CNS, central nervous system; FU, follow-up; IV, intravenous; N, number of participants; Nivo, nivolumab; PK, pharmacokinetic, Q2W, every 2 weeks; Q4W, every 4 weeks; RT, radiation therapy; SC, subcutaneous; vs, versus.

^a Treatment until recurrence of disease, unacceptable toxicity, participant withdrawal of consent, death, or a maximum of 52 weeks of treatment from first dose, whichever occurs first.

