5.1.4 Data Monitoring Committee and Other Committees

Data Monitoring Committee: A safety DMC will be implemented in this study to provide safety oversight throughout the course of Part 1 of the study. The DMC charter will describe the procedures related to the committee operations in greater detail. On 26-Oct-2022, enrollment was paused and a total of 14 participants had been randomized. On 24-Feb-2023, the study was terminated with no additional participants having been randomized. As this is an open-label study, the Sponsor will continue the safety monitoring of remaining participants in the study. No subsequent DMC meeting will occur.

Study Steering Committee: A Study Steering Committee (SSC) will be established to provide advisory oversight of the quality of the trial, with the objective of ensuring scientific integrity and the successful conduct of the CA2096GE Study. On 26-Oct-2022, enrollment was paused and a total of 14 participants had been randomized. On 24-Feb-2023, the study was terminated with no additional participants having been randomized. The Sponsor will continue to ensure the scientific integrity and successful conduct of the study. No SSC meeting will occur.

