10.4.2 Primary Endpoint(s)

Safety is the primary endpoint. See [Table 10.4.2-1](#) for details.

Table 10.4.2-1: Primary Endpoint

Primary Endpoint	Description	Timeframe

 • AEs/SAEs, treatment-related AEs/SAEs for each treatment group. 	
 • Incidence of all AEs/SAEs, treatment-related AEs/SAEs for each treatment group. 	
 • Up to 100 days after the last treatment of study intervention or up to discontinuation of study treatment.

Abbreviations: AE, adverse event; IMAE, immune-mediated adverse event; SAE, serious adverse event.

All safety analyses will be performed using the All Treated participants population.

The frequency of AEs, SAEs, and treatment-related AEs/SAEs will be tabulated by treatment arm. IMAEs, AEs, and SAEs leading to discontinuation of study drug, infusion/injection-related AEs, [REDACTED] deaths, and abnormalities in specific clinical laboratory assessments will be presented as listings by treatment arm.

The safety summary will be presented by severity where applicable. Analyses will be conducted using the 30 and/or 100-day safety window from the day of last dose received. AEs will be coded using the most recent Medical Dictionary for Regulatory Activities (MedDRA) version available during the conduct of the study. AEs and laboratory values will be graded for severity according to the NCI CTCAE version 5.0.

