immunogenicity and safety, a table summarizing the frequency and type of AEs of special interest may be explored by immunogenicity status.

In addition, potential relationships between immunogenicity and efficacy and/or PK may also be explored.

10.4.5.3 *Outcomes Research*

Not applicable per Protocol Amendment 01. The following information refers to the original study design.

Unless otherwise specified in the SAP, the analysis of Outcome Research endpoints will be performed on the All Treated participants population and will be restricted to treated participants who have an assessment at baseline and at least 1 post-baseline assessment for the given questionnaire (where applicable). Descriptive statistics will be provided.

10.4.5.4 *Biomarkers*

Not applicable per Protocol Amendment 01. The following information refers to the original study design.

For biomarker participants, descriptive summary statistics of biomarker assessments will be presented at baseline and at each on-study time point described in [Section 9.8](#), unless otherwise specified.

[figure not shown]
10.4.6 *Study Analyses Timeframe*

The following DBLs will be performed:

10.4.6.1 *Part 1*

Not applicable per Protocol Amendment 01. The following information refers to the original study design.

Primary lock for Part 1 will be performed after all randomized participants in both arms have completed PK evaluation for the co-primary endpoints (Week 17). Subsequent database lock(s) will occur at 18 and 36 months after last participant is randomized (minimum follow-up of 18 and 36 months for all randomized participants) to assess for longer safety and efficacy secondary endpoint of RFS.

10.4.6.3 *Final Analysis*

The DBL will occur approximately 100 days after the last participant last treatment or earlier as applicable due to participant death or lost to follow-up.

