10.5 Interim Analyses

Not applicable.

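### Does the leftover sponsor-blind sentence in Section 5.4.7 obstruct the Sponsor's safety monitoring now that the DMC has stopped meeting?

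*Combined protocol and SAP*

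**What the plan says.** Section 5.4.7, the rationale for open label, closes with the restriction: "The BMS study team will not conduct aggregate analyses by treatment group prior to pre-specified database locks (Sponsor blind approach". Unlike Sections 5.4.2 and 5.4.6, it is not marked as inapplicable under Amendment 01.

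Other current text bears on it:

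- Section 5.1 describes the study after the amendment: "Part 1 is no longer hypothesis-driven, but rather descriptive in nature", with safety and tolerability as the primary objective.
- Section 5.1.4 ends the committee's work ("No subsequent DMC meeting will occur") and passes the task on: "As this is an open-label study, the Sponsor will continue the safety monitoring of remaining participants in the study".
- Section 3.3.3 has the Sponsor assess benefit and risk continuously from all available data, attending among other things to "safety trends in this or any other clinical study of BMS-986298 or BMS-936558 whose severity and/or frequency suggest" an unreasonable risk to participants. Part of that sentence is redacted.
- Section 7.3 states that access to treatment assignment is not restricted.
- Section 10.4.2 defines the primary analysis: "The frequency of AEs, SAEs, and treatment-related AEs/SAEs will be tabulated by treatment arm".
- Section 10.4.6.1, with the Week 17, 18-month and 36-month locks, is marked not applicable, and Section 10.5 says the same of interim analyses. Section 10.4.6.3 leaves the final lock: "The DBL will occur approximately 100 days after the last participant last treatment", or earlier after death or loss to follow-up.

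**The concern.** The sponsor-blind sentence was written for a study with a PK non-inferiority test, several locks and a safety DMC. All three have gone. What remains is a prohibition that runs until the final lock, in a study whose primary analysis is itself a by-arm table of adverse events. Taken literally, the study team may not produce a cumulative by-arm count while participants are still being treated and followed. The body that might have done so no longer meets, and no visible sentence names another.

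The neighbouring rationale sections were marked as superseded and this one was not, which suggests an oversight. If the sentence did block the monitoring that Section 5.1.4 assigns to the Sponsor, an excess of events in the subcutaneous arm could go unremarked until the final lock. The remedy would look cheap: no hypothesis is tested, so by-arm looks cost no type I error.

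**Working it through.** The plan gives no figure to reproduce. The question is whether the provisions can all be followed together, and how much would be lost if the restriction were followed to the letter.

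**1. Who is barred from what**

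| Provision | Who | What |
|---|---|---|
| 5.4.7 | BMS study team | may not run aggregate analyses by arm before a lock |
| 5.1.4 | Sponsor | continues safety monitoring of the remaining participants |
| 3.3.3 | Sponsor | weighs benefit and risk continuously, using all available data |
| 7.3 | no limit stated | may see treatment assignment |
| 9.2.1, Appendix 3 | investigators to Sponsor | SAEs reported within 24 hours |

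Neither 5.1.4 nor 3.3.3 calls for a by-arm comparison, and 5.4.7 does not stop anyone reading individual cases with the arm visible. A Sponsor safety function outside the study team is not covered at all. Section 10.4.2 itself separates frequencies that are tabulated from items presented as listings by arm. Participant-level listings are therefore not plainly aggregate analyses. All five provisions can be followed at once.

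**2. Is the missing label evidence of leftover text?**

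Sections 5.4.2 (PK endpoints and margin) and 5.4.6 (patient-reported outcomes) were labelled because their subject was dropped. Section 5.4.1, on one-year treatment, carries no label because it still applies. The study is still open-label, so a rationale for open label still applies too. The missing label is weak evidence of an oversight.

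**3. How long the restriction lasts**

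Assumptions, chosen to give an upper bound: last participant randomized on 26-Oct-2022, the date enrollment paused (5.1.4); first dose 3 days later, the limit in the Schedule of Activities, so 29-Oct-2022; treatment completed. Amendment date 25-May-2023.

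- Last dose = first dose + offset, where the offset is 12 × 28 = 336 days (Arm B, Cycle 13 Day 1), 336 + 14 = 350 days (Arm A, Cycle 13 Day 15), or 52 × 7 = 364 days (the cap).
- Final lock = last dose + 100 days.

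| Case | Last dose | Days from amendment to last dose | Final lock | Days from amendment to lock |
|---|---|---|---|---|
| Arm B, C13D1 | 30-Sep-2023 | 128 | 8-Jan-2024 | 228 |
| Arm A, C13D15 | 14-Oct-2023 | 142 | 22-Jan-2024 | 242 |
| 52-week cap | 28-Oct-2023 | 156 | 5-Feb-2024 | 256 |

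Of the 228 to 256 days, 100 fall after the last dose. The period in which a by-arm count could bear on continued dosing is 128 to 156 days at most.

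**4. What a by-arm count could add**

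With 6 participants in Arm A and 8 in Arm B (5.2), take all events in Arm A. The two-sided Fisher probability is C(6,k)/C(14,k), because the opposite extreme table is more probable and is not added.

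- 3/6 versus 0/8: 20/364 = 0.055.
- 4/6 versus 0/8: 15/1001 = 0.015.
- The exact 95% interval for 3/6 is 12% to 88%.

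Only a gross imbalance would stand out. Three or four affected participants, all in one arm, would be obvious to anyone reading 14 openly assigned case histories.

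**5. Effect on the results**

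The primary tables are produced after the final lock. Their content does not depend on whether the study team counted events by arm beforehand.

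**The case for a change.** The strongest reply is that permission is not a remit. With the DMC stopped, no visible text makes cumulative by-arm review anyone's stated duty, and one live sentence tells the team closest to the data not to do it. The study team is not defined, so a cautious reader could take it to cover everyone at the Sponsor. No purpose is stated for keeping the blind in a descriptive study, and removing the sentence would cost almost nothing.

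Part of this stands. The documents do not say how the restriction and the monitoring role fit together, and one clarifying sentence would be harmless. Three things limit its weight.

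- The blind still has a sensible use. The primary endpoint includes treatment-related events, which rest on investigator judgement in an open-label trial. Section 9.2.2 asks for care not to introduce bias when events are collected. Keeping by-arm totals away from the team that queries those events is a defensible trade-off, and it does not depend on a hypothesis test.
- The text on remit is incomplete to an outside reader. Section 3.3.3 is redacted where it says what receives particular attention, so the absence of a named review cannot be established.
- The claim that only one lock remains needs a qualification. Section 10.4 still refers to a primary endpoint database lock without defining it separately, and the entry that would be Section 10.4.6.2 is redacted. With safety as the primary endpoint the two locks are probably the same, but the text does not say so.

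**Conclusion.** No change to the plan follows. Section 5.4.7 is poorly connected to Sections 5.1.4 and 3.3.3, but it does not contradict them. The gap is one that a Sponsor fills in ordinary practice, by case review with the arm known and by a safety function separate from the study team. Followed as written, the sentence leaves the final by-arm safety tables and their interpretation unchanged.

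No effect on participants is shown. The period at issue is at most 128 to 156 days of dosing after the amendment, assuming that the last participant was randomized on the day enrollment paused, started 3 days later and completed treatment; earlier randomization or early stopping shortens it. With 6 and 8 participants, a by-arm count adds almost nothing to an open listing.

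This rests on reading the study team as narrower than the Sponsor, which is how the two terms are used. If the Sponsor did apply the bar to all of its functions, the remedy would be a line of clarification and not a different analysis.
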